dosing regimen. Where available, individual ECLIA-based anti-CZP antibody data will be tabulated by study visit and Baseline age stratum (all study participants, 2 to 5 years, 6 to 11 years, and 12 to 17 years). In addition, safety and efficacy profiles by antibody titers (or titer categories) may be investigated.

Change #140

Section 13.5, paragraph 5, bullets 14 and 15:

- Change from Baseline on FPS-R (child-reported, for subjects ages 5 to 11 years), daily during the first 7 days of treatment; Weeks 4, 12, 16, and 24; and then every 8 weeks thereafter through the Early Discontinuation/End of Treatment Visit. Following Protocol Amendment 8, change from Baseline on FPS-R is assessed every 16 weeks.
- Change from Baseline in JIA Pain VAS, daily during the first week of the study (acute and standard versions); Weeks 4, 12, 16, and 24; and then every 8 weeks thereafter through the Early Discontinuation/End of Treatment Visit (standard version) for subjects ages 12 to 17 years. Following Protocol Amendment 8, change from Baseline in JIA Pain VAS is assessed every 16 weeks.

Has been changed to:

- Change from Baseline on FPS-R (child-reported, for study participants ages 5 to 11 years), daily during the first 7 days of treatment; Weeks 4, 12, 16, 24, and then every 8 weeks thereafter (for study participants enrolled prior to Protocol Amendment 9, visit frequency changes to every 16 weeks instead of every 8 weeks following implementation of Protocol Amendment 8) through the Early Discontinuation/End of Treatment Visit.
- Change from Baseline in JIA Pain VAS, daily during the first week of the study (acute and standard versions); Weeks 4, 12, 16, 24, and then every 8 weeks thereafter (for study participants enrolled prior to Protocol Amendment 9, visit frequency changes to every 16 weeks instead of every 8 weeks following implementation of Protocol Amendment 8) through the Early Discontinuation/End of Treatment Visit (standard version) for study participants ages 12 to 17 years.

Change #141

Section 13.7, the following text was added:

A futility analysis of the PedACR30 response rate was performed after all active study participants enrolled on the reduced CZP dose had completed the Week 16 (Visit 8) assessments. If less than 50% of the study population enrolled on the reduced CZP dose regimen (Protocol Amendment 5) achieved a PedACR30 response at Week 16, the study was to be discontinued. The futility analysis confirmed that $\geq 50\%$ of the study population enrolled on the reduced CZP dose regimen achieved a PedACR30 response at Week 16. Given the descriptive nature of the data presentations, there were no statistical implications of this interim analysis. A further futility analysis will not be performed using the additional subjects that will be enrolled on the original CZP dose regimen following the implementation of Protocol Amendment 9.

In addition to the futility analysis, several interim analyses were planned, including interim analyses of PK data, and full interim analyses of PK, immunogenicity, safety, and efficacy endpoints, as described below.

Change #142

Section 13.7, paragraph 1 and 2, the following text was removed:

Interim analysis of PK data will compare CZP plasma concentration data from this study with CZP plasma concentrations observed previously in adult subjects with RA. Interim analysis of CZP plasma concentrations was started when 6 subjects in 1 of the age groups completed Week 12 (Visit 7).

Comparisons will be made between the Week 12 geometric mean and median values for the pediatric and adult subjects, as well as between the individual pediatric data and the adult 5th and 95th percentile and minimum and maximum observed values.

Change #143

Section 13.7, paragraph 3:

If the pediatric plasma concentrations demonstrate that the geometric mean and median concentrations are below the adult 5th percentile or above the 95th percentile, the PK data will be used to re-evaluate the weight-based dose adjustment algorithm for pediatric subjects. Interim CZP plasma concentration data available at the time of Protocol Amendment 3 indicated that no change to the dosing algorithm was required. The protocol stated that if future interim analyses, which may include PopPK, indicate that plasma concentrations of JIA subjects are outside of the exposure range observed in previous adult RA studies, a revised pediatric dose algorithm will be derived. Any change in dose regimen will require a protocol amendment prior to implementation.

Based on results of an interim PopPK analysis conducted in Jun 2013 described in Section 5.1, the dosing regimen will be changed with Protocol Amendments 4 and 5, and the doses to be administered will be reduced by 50% for all weight groups. This change is intended to achieve plasma concentrations similar to the effective concentrations observed in previous studies in adult subjects with RA.

Has been changed to:

Per original protocol, if the pediatric plasma concentrations demonstrate that the geometric mean and median concentrations are below the adult 5th percentile or above the 95th percentile, the PK data will be used to re-evaluate the weight-based dose adjustment algorithm for pediatric study participants. Interim CZP plasma concentration data available at the time of Protocol Amendment 3 indicated that no change to the dosing algorithm was required. The protocol stated that if future interim analyses, which may include PopPK, indicate that plasma concentrations of JIA study participants are outside of the exposure range observed in previous adult RA studies, a revised pediatric dose algorithm will be derived. Any change in dose regimen will require a protocol amendment prior to implementation.

An interim analysis of PK data conducted following Protocol Amendment 3 compared CZP plasma concentration data from this study with CZP plasma concentrations observed previously in adult study participants with RA. Interim analysis of CZP plasma concentrations was started when 6 study participants in 1 of the age groups completed Week 12 (Visit 7). Comparisons were made between the Week 12 geometric mean and median values for the pediatric and adult study participants, as well as between the individual pediatric data and the adult 5th and 95th percentile and minimum and maximum observed values.

Based on results of this interim PopPK analysis (also described in Section 5.1), the dosing regimen was changed with Protocol Amendments 4 and 5, and the doses to be administered were reduced by 50% for all weight groups. This change was intended to achieve plasma concentrations similar to the effective concentrations observed in previous studies in adult study participants with RA.

Change #144

Section 13.7, paragraph 5, 6, 7:

For the Week 24 interim clinical study report, the CZP plasma concentrations were monitored following the change in dose regimen to confirm they were within the targeted adult range. Following Protocol Amendment 8, no more interim PK analyses will be performed, and the final PK data to be reported will use a new MSD assay, and consequently no further comparison will be performed with respect to the adult RA concentrations range.

After all active subjects have completed the Week 16 (Visit 8) assessments, an interim analysis of PedACR30 response rates will be performed and the study will be discontinued if less than 50% of the study population enrolled on the reduced CZP dose regimen (Protocol Amendment 5) achieves a PedACR30 response at Week 16. Given the descriptive nature of the data presentations, there are no statistical implications of this interim analysis.

After the last subject has reached the Week 24 Visit (Visit 10), the database will be cut and a full interim analysis of all safety and efficacy endpoints will be performed based upon 24 weeks of exposure for each individual (or all data for those cases who withdrew before this timepoint).

Has been changed to:

An interim analysis of PK, immunogenicity, safety, and efficacy endpoints was performed after all active study participants that were enrolled and treated prior to implementation of Protocol Amendment 9 had completed the Week 24 (Visit 10) assessments, and the results were reported separately. An interim analysis, including all enrolled participants, for all PK, immunogenicity, safety, and efficacy endpoints will be performed after all active study participants, including those enrolled following the implementation of Protocol Amendment 9, have completed the Week 24 (Visit 10) assessments.

Change #145

Section 13.8, paragraph 1:

Based upon the ICH guideline for the assessment of safety, it is planned to enroll a sufficient number of subjects to this study to have a minimum of 100 with at least 12 months continuous exposure to CZP. Assuming a dropout rate of approximately 20%, it was originally determined that 125 subjects would need to be enrolled. At the time of Protocol Amendment 5, 78 subjects had been enrolled according to the original CZP dose regimen, and it is planned to enroll a further 78 subjects on the reduced CZP dose regimen, so that a comparable number of subjects on the reduced CZP dose regimens can be analyzed. Thus, the total number of subjects planned to be enrolled will be increased to 156 subjects. Assuming a Screening failure rate of 25%, it is planned to screen 195 subjects in total.

Has been changed to:

Based upon the ICH guideline for the assessment of safety, it is planned to enroll a sufficient number of study participants to this study to have a minimum of 100 with at least 12 months continuous exposure to CZP. Assuming a dropout rate of approximately 20%, it was originally determined that 125 study participants would need to be enrolled. At the time of Protocol Amendment 5, 78 study participants had been enrolled according to the original CZP dose regimen, and it was planned to enroll a further 78 study participants on the reduced CZP dose regimen, so that a comparable number of study participants on the reduced CZP dose regimens could be analyzed. Thus, the total number of study participants planned to be enrolled was increased to 156 study participants. Assuming a Screening failure rate of 25%, it is planned to screen 195 study participants in total.

Change #146

Section 13.8, the following text has been added:

With Protocol Amendment 9, an additional 30 study participants will be enrolled on the original dose regimen with the aim to enroll at least 5 study participants in each weight range of 10 to <20kg (22 to <44lb), 20 to <40kg (44 to <88lb), and ≥ 40 kg (≥ 88 lb).

Change #147

Section 16, the following reference has been added:

FDA Guidance for Industry – Bioanalytical Method Validation. 2018.

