TB screening: Interferon-gamma release assay (IGRA) testing (QuantiFERON®) is required to be performed by the central lab for all study participants from 5 to 17 years of age. TST and IGRA testing at Screening is mandatory for study participants less than 5 years of age in this study unless written documentation of BCG vaccination is available (refer to Section 6.2 [exclusion criterion 11] and Section 10.7.9). Following implementation of Protocol Amendment 7, IGRA testing (QuantiFERON) should be done once a year (approximately every 48 weeks) for all study participants.

Change #37

Section 5.2, Schedule of study assessments, Table 5-1, footnote o

A chest radiograph (anterior-posterior view at minimum, but preferably anterior-posterior and lateral) must be taken if the subject has a positive IGRA/PPD testing at Screening or, if written documentation of BCG vaccination is available for subjects ages 2 to 4 years, a TB questionnaire indicating an increased subject's risk of exposure or infection with TB. If a subject has had a recent radiograph of the chest within approximately 3 months prior to Screening, it may be used in lieu of the protocol-required radiograph. All chest imaging must be read by a qualified radiologist/pulmonary physician who is specifically required to look for evidence of active TB or inactive TB. Refer to Section 10.7.9.2.2 for further information on chest x-rays.

Has been changed to:

Chest radiographic imaging is done at Screening and results must be available at Baseline before first drug administration unless a chest x-ray or CT is available within 2 months prior to Screening.

Change #38

Section 5.2, Schedule of study assessments, Table 5-1, footnote q

For subjects ages 5 to 11 years. Daily assessment during the first week (Baseline and Day 1 to Day 7, to be collected at Week 1). In addition, to be completed at Weeks 4, 12, 16, 24, and then every 8 weeks thereafter (every 16 weeks following Protocol Amendment 8) through the End of Treatment/Early Discontinuation Visit.

Has been changed to:

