Subjects with known TB infection, or at high risk of acquiring TB infection, are excluded. Subjects with latent TB (LTB) infection that have not received a minimum of 4 weeks of prophylactic treatment are only eligible following prophylaxis:

- a. Known TB infection whether present or past is defined as:
 - Active TB infection or clinical signs and symptoms suspicious for TB (pulmonary or extra-pulmonary)
 - History of active TB infection involving any organ system or findings in other organ systems consistent with TB infection
 - Any evidence by radiography or other imaging modalities consistent with previously active TB infection that is not reported in the subject's medical history
- b. High risk of acquiring TB infection is defined as:
 - Known exposure of Subject or Caregiver to another person with active TB infection within the 3 months prior to Screening
 - Time spent in a healthcare delivery setting or institution where individuals infected with TB are housed and where the risk of transmission of infection to Subject or Caregiver is high
- c. Latent TB infection is defined as:

Absence of signs, symptoms (ie, evidence of organ-specific involvement), or physical findings suggestive of TB infection with a positive interferon-gamma release assay (IGRA [QuantiFERON]) test (or 2 indeterminate IGRA test results) or positive PPD (where the PPD skin test is approved for use by UCB; mandatory for ages 2 to 4 years in this study) or, if written documentation of Bacille Calmette-Guérin (BCG) vaccination is available for subjects ages 2 to 4 years, a TB questionnaire indicating an increased subject's risk of exposure or infection with TB, and a chest x-ray (or other imaging) without evidence of TB infection.

Note: If available, respiratory or other specimens must also be smear and culture negative for TB (Centers of Disease Control and Prevention [CDC] diagnosis of LTBI infection, <http://www.cdc.gov/TB/topic/testing/default.htm>).

Refer to Section 10.7.9 for additional information on TB definition and clinical signs, diagnosis, documentation, and treatment.

Subjects with a history of or active infection with nontuberculous mycobacteria (NTMB) are excluded from this study.

Has been changed to:

Participant has:

- a. Known active TB disease
- b. History of active TB involving any organ system
- c. History of or current latent tuberculosis infection (LTBI)
- d. High risk of exposure to TB infection

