TB screening: TST and IGRA for study participants from 2 to 4 years of age (unless the study participant is located in a country with high TST positivity and/or written documentation for BCG vaccination is available) or IGRA (to be performed by the central lab) for study participants from 5 to 17 years of age. Note that the TST may be positive due to BCG vaccination, however, UCB will not permit enrollment of pediatric study participants <5 years old into the study without written approval from a physician with expertise in pediatric TB**

Change #80

Section 8.2

- CZP plasma concentrations and anti-CZP antibodies

Has been changed to:

- CZP plasma concentrations
- Anti-CZP antibodies

Change #81

Section 8.3

- CZP plasma concentrations and anti-CZP antibodies(Week 1 only)

Has been changed to:

- CZP plasma concentrations (Week 1 only)
- Anti-CZP antibodies (Week 1 only)

Change #82

Section 8.4

- CZP plasma concentrations and anti-CZP antibodies (Weeks 4, 12, 16, and 24 only, OR if a dose change is performed at the current visit OR if the subject's dose was changed during 1 of the last 3 visits following Protocol Amendment 4; predose. Subjects will return to the clinic site for a **postdose CZP plasma sample** approximately **5 to 7 days following the Week 16 visit.**)

Has been changed to:

- CZP plasma concentrations (predose at Weeks 4, 12, 16, and 24. Study participants will return to the clinic site for a **postdose CZP plasma sample** approximately **5 to 7 days following the Week 16 visit.**)
- Anti-CZP antibodies (predose at Weeks 4, 12, 16, and 24)

Change #83

Section 8.4, last paragraph

Documentation of the **Week 16 and Week 24** assessment of all 6 core set measures of PedACR response (PRINTO/PRCSG standard joint examination, Physician's Global Assessment of Disease Activity [VAS], CHAQ-parent reported, Parent's Assessment of Arthritis Pain [VAS], Parent's Global Assessment of Overall Well-Being [VAS] and CRP) **will be submitted to UCB or designee for immediate review of completeness, while the subject is still on site.**

Has been changed to:

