Hematology, biochemistry, and urinalysis samples will be collected at Screening, Baseline, Weeks 4, 8, 12, 16, 20, 24, 32 and every 8 weeks thereafter (for study participants enrolled prior to Protocol Amendment 9, visit frequency changes to every 16 weeks instead of every 8 weeks following implementation of Protocol Amendment 8), the Early Discontinuation/End of Treatment Visit, and the Final Visit 12 weeks after the last dose of study medication. At Week 1, only CRP and PK samples will be collected and at Week 2, only CRP samples will be collected. In addition, hematology, biochemistry, and CRP samples will be collected at Unscheduled Visits for study participants undergoing a dose change (Section 7.2.1 and Section 8.6.1).

Change #109

Section 10.6, paragraph 1, sentence 3:

In addition, hematology, biochemistry, and CRP samples will be collected at Unscheduled Visits related to the dose change implemented with Protocol Amendment 4.

Has been changed to:

In addition, hematology, biochemistry, and CRP samples will be collected at Unscheduled Visits for study participants undergoing a dose change (Section 7.2.1 and Section 8.6.1).

Change #110

Section 10.6, paragraph 9:

If IGRA testing is required to be performed by the central lab (for all subjects from 5 to 17 years of age, see Section 6.2) additional blood sampling of approximately 3mL will be required at Screening.

Has been changed to:

The TB assessment by IGRA testing is required to be performed by the central lab; additional blood sampling of approximately 3mL will be required at Screening.

Change #111

Section 10.6, paragraph 10:

If the result of the IGRA is indeterminate, the test may be repeated once. The retest must be conducted in the allowable Screening window. Subjects with IGRA (performed ≤ 3 months prior to Screening) positive or indeterminate and a chest x-ray confirmative of TB infection are excluded (see Section 10.7.9.2).

Has been changed to:

If the result of the IGRA test is indeterminate, the test may be repeated once. If positive or indeterminate on retest, the study participant must not be enrolled (Section 10.7.9.5).

Change #112

Section 10.6, paragraph 11 and 12

For subjects from 2 to 4 years of age, PPD testing will be performed locally (except for subjects with documented BCG vaccination) as described in Section 10.7.9.2.4.

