During the study and upon implementation of Protocol Amendment 7, IGRA testing should be done once a year (approximately every 48 weeks) for all subjects from 5 to 17 years of age. For subjects from 2 to 4 years of age, both IGRA and PPD testing should be performed once a year (approximately every 48 weeks). In cases where written documentation of BCG vaccination is available or previous PPD test was positive, only IGRA should be performed.

Has been changed to:

For study participants from 2 to 4 years of age, TST and IGRA testing will be performed (except for study participants with documented BCG vaccination) as described in Section 10.7.9.8.2. In countries with high BCG vaccination or high TST positivity, only IGRA should be performed (Section 10.7.9.8.2). The TST may be positive due to BCG vaccination, however, UCB will not permit enrollment of pediatric study participants < 5 years old into the study with written approval from a physician with expertise in pediatric TB. IGRA testing should be done once a year (approximately every 48 weeks) for all study participants.

Change #113

Section 10.6, Table 10-2:

| Hepatitis screening ^(c) |
|------------------------------------|
| HBcAb |
| HBsAb |
| HBsAg |
| HCVAb |
| HBV DNA, if applicable |
| TB screening ^(d) |
| IGRA, PPD |

Has been changed to:

| Hepatitis screening ^(c) |
|------------------------------------|
| HBcAb |
| HBsAb |
| HBsAg |
| HCVAb |
| HBV DNA, if applicable |
| HCV RNA, if applicable |
| TB screening ^(d) |
| IGRA, TST |
| HIV Screening |
| HIV antigen or antibody |

Change #114

Section 10.6, Table 10-2, footnote C:

Subjects will be tested for hepatitis at Screening. HBV DNA is required for subjects with only positive HBcAb (negative HBsAg and HBsAb) or only positive HBsAg. A hepatitis panel result which indicates immunity due to hepatitis B vaccination is not considered an exclusion criterion.

Has been changed to:

At Screening, laboratory testing includes testing for hepatitis B core antibody, hepatitis B surface antibody, hepatitis B surface antigen, hepatitis C virus antibody, and HIV 1/2. Study participants with a positive HBV test will not be allowed in the study (except for anti-hepatitis B positive only, in case study participant is immune due to well-documented

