As TNF inhibitors are known to be associated with significant risk of reactivation of LTBI or previously treated active TB, appropriate rigorous precautions are being taken within the protocol (see Section 6.2 [Exclusion Criterion 11] and Section 6.4 [Withdrawal Criterion 2]).

Study participants with known active TB disease, at high risk of acquiring TB infection, or with past or current LTBI or current or history of NTMB infection are excluded from the study.

- a. Known TB infection whether present or past is defined as:
 - Active TB infection or clinical signs and symptoms strongly suggestive of TB (pulmonary or extra pulmonary).
 - History of active TB infection involving any organ system or findings in other organ systems consistent with TB infection.
 - Any evidence by radiography or other imaging modalities consistent with previously active TB infection that is not reported in the participant 's medical history.
- b. High risk of acquiring TB infection is defined as:
 - Known close exposure (eg, sleeping in the same room) to another person with active TB infection within 3 months prior to Screening.
 - Time spent within 3 months prior to Screening in a healthcare delivery setting or institution where individuals infected with TB are housed or where the risk of transmission of infection is high.
- c. LTBI is defined as an infection by mycobacteria tuberculosis with:
 - A positive IGRA (or 2 indeterminate IGRAs), AND
 - Chest imaging (or other imaging) negative for TB infection, AND
 - Absence of signs, symptoms (eg, evidence of organ-specific involvement), or physical findings suggestive of TB infection.
- d. Pulmonary NTMB infection is defined as a group of lung infections caused by mycobacteria different from mycobacterium tuberculosis infections.

Change #120

Section 10.7.9.1, Section 10.7.9.2, Section 10.7.9.3 have been removed

Change #121

Section 10.7.9.1, Section 10.7.9.2, Section 10.7.9.3, Section 10.7.9.4, Section 10.7.9.5, Section 10.7.9.6, Section 10.7.9.7 have been added.

Change #122

Section 11.1, last paragraph:

Documentation of the assessment of all 6 core set measures will be submitted to UCB or designee for immediate review of completeness at Week 0 (Baseline), Week 16, Week 24, and Week 56, while the subject is still on site.

Has been changed to:

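### Amendment 9 contradicts itself on whether IGRA is waived at Screening for children under 5 with documented BCG vaccination, although IGRA is the only test in the latent-TB exclusion definition

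*Protocol*

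**What the plan says.** All the text at issue is replacement wording introduced by Protocol Amendment 9 (Section 17.19), the latest amendment shown. The comparison is therefore between passages of one amendment, not between old and new text.

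- **Table 5-1, footnote n (Change #36):** "TST and IGRA testing at Screening is mandatory for study participants less than 5 years of age in this study unless written documentation of BCG" (that is, unless a BCG record exists).
- **Section 8.1, Screening (Change #79):** TST and IGRA for ages 2 to 4, "unless the study participant is located in a country with high TST positivity and/or written documentation for BCG vaccination is available".
- **Section 10.6, sentence on ages 2 to 4 (Change #112):** "TST and IGRA testing will be performed (except for study participants with documented BCG vaccination").
- **Section 10.6, the next sentence (Change #112):** "In countries with high BCG vaccination or high TST positivity, only IGRA should be performed".
- **Section 10.6, general statement (Change #110):** "The TB assessment by IGRA testing is required to be performed by the central lab", with about 3mL of additional blood at Screening. The former limit to ages 5 to 17 was deleted.
- **Section 6.2, criterion 11c (Change #55):** excludes "History of or current latent tuberculosis infection (LTBI").
- **Section 10.7.9, definition of LTBI (Change #119):** the first of three joint conditions is "A positive IGRA (or 2 indeterminate IGRAs), AND". The other two are imaging negative for TB and absence of signs, symptoms or physical findings.

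**The concern.** The BCG exception is attached to the pair of tests, not to the TST alone. Two statements in Section 10.6 point the other way for IGRA. Two sites reading different parts of the same amendment could therefore screen the same child differently.

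This is an entry safety gate for a TNF inhibitor. Section 10.7.9 itself cites the risk of reactivating latent infection as the reason for strict precautions. If IGRA is skipped, the one test named in the definition behind criterion 11c is missing, and current latent infection cannot be established at Screening.

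**Working it through.** No arithmetic applies: the protocol gives no figure to reproduce on this point. The check sets the rules side by side for three kinds of child, each read literally.

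| Rule | A: documented BCG, country with neither high BCG vaccination nor high TST positivity | B: age 2 to 4, no documented BCG, high-TST country | C: documented BCG, age 2 to 4, high-BCG or high-TST country |
|---|---|---|---|
| Table 5-1 footnote n | neither test required | both required | neither required |
| Section 8.1 | neither | neither | neither |
| Section 10.6, ages 2 to 4, first sentence | neither | both | neither |
| Section 10.6, next sentence | silent | IGRA only | IGRA only |
| Section 10.6, general statement | IGRA | IGRA | IGRA |

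1. **Child B** gets three different answers: both tests, neither test, or IGRA alone. **Child C** gets two: neither, or IGRA alone. In **child A** the conflict is between the exception and the general IGRA statement only, because the IGRA-only sentence depends on the country and does not clearly reach this child.

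2. **Link to the exclusion.** The LTBI definition joins its three conditions by AND. With no IGRA result, the first condition cannot be met, so current LTBI cannot be established whatever the other findings are. The history part of criterion 11c can still be met from the medical record.

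3. **Imaging cannot substitute.** Amendment 9 makes chest imaging at Screening general (footnote o, Change #37; Section 8.1, Change #78). The LTBI definition requires that imaging to be negative, so imaging cannot identify the condition.

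4. **The former alternative is gone from the definition.** The superseded criterion 11c let "a TB questionnaire indicating an increased subject's risk of exposure or infection with TB" stand in for a test in BCG-vaccinated children aged 2 to 4. The current definition has no such route. This is context for the gap; its removal is not itself an error.

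5. **The specialist safeguard is also contradictory.** Section 8.1 bars enrollment under age 5 *without* written approval from a physician with expertise in pediatric TB. The matching sentence in Section 10.6 bars it *with* such approval.

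6. **Timing.** IGRA is repeated yearly, at about 48 weeks. The TB questionnaire is completed at Weeks 12 and 24 and every 16 weeks thereafter, and suspicion leads to TB testing and/or a chest x-ray (Table 5-1 footnote i). Week 48 is therefore the latest routine IGRA, not a fixed untested period.

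**The case against.** The strongest reply is that no waiver of IGRA was intended. The superseded Screening rule waived only the skin test, and the superseded yearly rule kept IGRA alone when BCG was documented. Section 10.6 still says IGRA only for certain countries, and its general statement carries no BCG limit. Section 10.6 also refers the rule for ages 2 to 4 to Section 10.7.9.8.2, which may settle the matter. Entry is not ungated in any case: active TB, past TB and high exposure risk remain separate exclusions, chest imaging is general, and Section 8.1 requires specialist approval.

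Much of this stands. A drafting slip is plausible, and a reader should not infer that the plan lets the youngest children in general enter untested. The exception reaches only children under 5 with documented BCG and, in Section 8.1, those aged 2 to 4 in high-TST countries. Other current text keeps IGRA for at least some of them.

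The reply does not remove the contradiction. Footnote n and Section 8.1 are what a site uses to schedule Screening, and a clarification elsewhere would leave their opposite instruction in place. The general statement in Section 10.6 can also be read as saying where the assay is run rather than who receives it, so it is a weak basis for overriding the exception. The other safeguards do not supply the result that the LTBI definition needs.

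**Conclusion.** The contradiction is real and should be corrected. Three current passages waive TST and IGRA together for documented BCG, two keep IGRA, and the exclusion definition rests on IGRA as its only test. A site following footnote n or Section 8.1 literally could dose such a child with no Screening result able to establish current LTBI.

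Size: unknown. Amendment 9 adds 30 participants and aims for at least 5 in the 10 to <20kg band, but it gives neither the number under 5 nor the share with documented BCG, which could be anything from 0 to 100%.

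Three stronger inferences are not supported:

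- **About 48 weeks without a test.** This is only the routine maximum, because the questionnaire can prompt testing earlier.
- **A positive TST has no bearing on eligibility.** The TST is absent from the LTBI definition shown, but its handling may be set out in sections not available.
- **Bias in the primary safety variable.** An infection present at entry but found later could be counted as a TEAE leading to permanent withdrawal of IMP. The chain is possible, but nothing in the protocol sizes it.

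The conclusion assumes that the Amendment 9 replacement wording is the text in force. Only the second part of the protocol was available, and the full text of Sections 10.7.9.1 to 10.7.9.8 is not in it.

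**What to change.** Reconcile Table 5-1 footnote n, Section 8.1, Section 10.6 and the LTBI definition in Section 10.7.9, as follows:

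- State one rule, separately for TST and for IGRA, on what documented BCG vaccination changes and what location in a high-BCG or high-TST country changes.
- Make the Screening schedule and the exclusion definition agree. This can be done by changing either one.
- Reconcile the *with* and *without* wording on written specialist approval between Sections 10.6 and 8.1.
- Check the result against Sections 10.7.9.1 to 10.7.9.8, including 10.7.9.8.2, to which Section 10.6 refers.

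Which testing rule stands is for the sponsor's TB experts to decide; this review does not propose one. The cost is wording in four places, plus notice to sites. Whether any child's Screening procedures change depends on the rule chosen. Section 10.6 already states a Screening IGRA sample of about 3mL.
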